9.7.4.4. Sensitivity analyses

A concern with observational data is confounded by unmeasured or uncontrolled confounders; that is, could an unobserved factor related to both the treatment and outcome of interest explain an association, in the absence of a true causal effect. Sensitivity analyses are useful in assessing how robust an association is to potential unmeasured or uncontrolled confounding and are important tools to evaluating evidence for causation in the face of unmeasured confounding. Sensitivity analyses consider how strong unmeasured confounding would have to be to explain away the association, that is, how strongly the unmeasured confounder would have to be associated with the treatment and outcome for the treatment—outcome association not to be causal. Sensitivity analyses of missing data are also critical to evaluating the sensitivity of conclusions to violations in missing data assumptions. The following sensitivity analyses will be performed for the primary endpoint:

Propensity score matching (PSM) will be used as a sensitivity analysis to control
confounding. Propensity score matching creates sets of patients for treatment and
control cohorts. A matched set consists of at least 1 patient in the treatment group and
1 in the control group with similar propensity scores. The goal is to approximate a
random clinal trial, eliminating many of the problems that come with observational
data analysis. Matches will be made using 1:1 nearest neighbor matching without
replacement.

- Sensitivity analyses with the definition of the line of regimen by A1122 (i.e., the combination drugs were given within 28 days).
- Other sensitivity analyses may be conducted as needed, which will be described in the SAP.

9.7.4.5. Subgroup analyses

 Subgroup analyses will be conducted according to age, minority, ECOG performance, de novo metastatic, visceral, non-visceral, bone only, disease sites, endocrine sensitivity, endocrine AI partner, comorbidities, subsequent treatments as appropriate based on availability of the data and sample sizes.

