be used to compute a propensity-to-treatment score (PS) by a logistic regression model, where the outcome variable is being in the palbociclib + AI group (yes, no). The individual PS is used to obtain the individual IPTW which is applied to the observations to assess the balance between treatment arms in the potential confounders after weighting.

If the method of IPTW yields balanced treatment groups with respect to the potentially measured confounders, then a weighted log-rank test using IPTW will be used to compare OS between the palbociclib + AI group and the AI alone group, with a nominal p< 0.05, two-sided, indicating an OS benefit in the palbociclib + AI group. The weighted Cox proportional hazards model will be used to compute the hazard ratio and the corresponding 95% CI. If the method of IPTW does not yield balanced treatment groups with respect to the potential confounders, analysis by PS quintiles will be used. All subjects will be stratified in quintiles based on the PS. A stratified log-rank test (stratified by PS quintiles) will be used to compare OS between the palbociclib + AI group and the AI alone group, with a nominal p< 0.05, two-sided, indicating an OS benefit in the palbociclib + AI group. This method allows for the comparison of subjects with similar PS without the potential loss of subjects in 1-1 matching. A stratified Cox proportional hazards model (stratified by PS quintiles) will be used to compute the hazard ratio and the corresponding 95%CI.

These time-to-event endpoints will also be summarized using the weighted Kaplan-Meier method and displayed graphically where appropriate. Similar analyses will be performed for rwPFS. Logistic regression analysis will be performed to compare rwTR between the 2 treatment groups. Descriptive analyses will be performed to report baseline patient demographics and clinical characteristics, treatment patterns, and time to next line of systemic anticancer therapy from palbociclib + AI initiation. Subgroup analyses will be conducted according to age, ethnicity, ECOG performance, metastatic site (i.e. visceral, bone only, etc.), and endocrine sensitivity as sample sizes allow.

A detailed statistical analysis plan (SAP) will be developed separately.

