The pre-specified analysis of patients who were endocrine sensitive demonstrated an OS HR of 0.72; 95% CI: 0.55, 0.94 in those without sensitivity to previous endocrine treatment (HR of 1.14; 95% CI; 0.71, 1.84). The Phase 3 PALOMA-2 study confirmed the findings from the PALOMA-1 trial, demonstrating a median PFS in the palbociclib + letrozole arm of 24.8 months compared to 14.5 months in the placebo + letrozole arm (HR of 0.58; 95% CI: 0.46, 0.72; 1-sided p<0.001)⁵. With extended follow-up, the median PFS was 27.6 vs 14.5 months; P<0.0001; data cutoff: May 31, 2017)⁴. Subgroup PFS analyses according to stratification factors and demographic characteristics or prognostic factors revealed consistent results in PALOMA-2⁵ and PALOMA-3 trial^{22, 23} in all studied subgroups. Results for the secondary endpoint of OS data from PALOMA-2 are event driven and not yet available.

Of note, a patient population *not* included in the PALOMA-1 or -2 trials investigating palbociclib + letrozole as first line treatment for women with ER+/HER2- advanced disease was the pre or perimenopausal population. The PALOMA-3 study investigating palbociclib + fulvestrant did include pre or perimenopausal patients, however the study evaluated patients who were progressed following endocrine therapy. The subgroup of 108 pre or perimenopausal women (out of the total 521) randomized to palbociclib + fulvestrant + goserelin versus placebo + fulvestrant + goserelin in a 2:1 fashion showed a statistically longer median PFS of 9.5 versus 5.6 months respectively (HR of 0.50; 95% CI: 0.29, 0.87)²⁴. The safety profile from the PALOMA-2 and -3 trials were consistent, with no new safety signals identified across the Phase 3 studies. Long-term pooled safety analyses of the 3 randomized Phase 2 and 3 studies demonstrated no evidence of specific cumulative or delayed toxicities with palbociclib + endocrine therapy.²⁵ The primary toxicity of palbociclib is neutropenia, which can be managed with dosing interruption and/or dose reduction.

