Understanding the effectiveness of new treatments in diverse clinical practice as a complement to RCT data is important as this provides evidence of the clinical benefit of these treatments in a more heterogeneous population with comorbid conditions and variations in care delivery seen in routine clinical practice ^{7,8}. Accumulating evidence has demonstrated real-world safety and effectiveness of palbociclib in combination with endocrine therapy since its approval in February 2015. For example, in a retrospective chart review¹¹, the palbociclib + AI treatment landmark analyses showed that 84.1% of patients were progression free and 95.1% were alive at 12 months.

A total of 1,430 female patients

with HR+/HER2-MBC in the first line setting were included in the analysis. The analysis demonstrated that first-line palbociclib plus letrozole versus letrozole alone significantly prolonged patients' median rwPFS (20.0 vs 11.9 months; hazard ratio, 0.58 [95% CI, 0.49–0.69]; P<0.0001) and overall survival (OS) results (median OS not reached vs 43.1 months; hazard ratio, 0.66 [95% CI, 0.53–0.82]; P<0.001) ¹⁹. Furthermore, tumor response analysis demonstrated that the real-world best tumor response rate was 58.6% in the palbociclib plus

letrozole group versus 39.1% in the letrozole group (odds ratio, 2.21 [95% CI, 1.50–3.25], P<0.0001) after propensity score matching (PSM), suggesting that HR+/HER2– MBC patients were more likely to respond to palbociclib plus letrozole compared to letrozole alone¹².

In another retrospective analysis of Flatiron database, Downer et al included 5,259 HR+/HER2- patients diagnosed with MBC9. Median overall survival was longer in patients receiving CDK 4/6 inhibitor (palbociclib, ribociclib, and abemaciclib) in combination with endocrine therapy (ET) than for patients receiving ET alone, or chemotherapy. Patients receiving CDK 4/6 in combination with ET compared to ET alone demonstrated a HR of 0.73 (95% CI: 0.65, 0.83) using multivariable Cox proportional hazards models. The median OS in the CDK4/6 inhibitor arm was 44.9 months (95% CI: 40.8, NA) versus 35.8 months (95% CI: 33.1, 38.9) in the ET alone arm versus 24.2 months (95% CI: 22.2, 26.9) in chemotherapy arm. Palbociclib, the first approved CDK 4/6 inhibitor, comprised 94% of CDK 4/6 inhibitor use in the study.

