8. RESEARCH QUESTION AND OBJECTIVES

This study aims to assess real-world effectiveness in HR+/HER2- MBC patients initiating palbociclib + AI or AI alone as first-line therapy during the period 01 February2015 through March 2020.

Primary Objective

• To compare overall survival (OS) of first line palbociclib + AI versus AI alone for postmenopausal women or men with HR+/HER2- MBC

Secondary objectives

- To compare real-world progression free survival (rwPFS) and real-world tumor response (rwTR) of first line palbociclib + AI versus AI alone for postmenopausal women or men with HR+/HER2- MBC
- To describe treatment patterns of Palbociclib, including initial dose, dose adjustment, treatment duration, subsequent treatments, and time to chemotherapy

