3.2. Statistical decision rules

The alpha level will be 0.05, 2-sided. No adjustments for multiple comparisons will be made.

3.3. sample size calculation

Approximately 3000 patients will be included with close to a 1:1 ratio between palbociclib + AI and AI alone cohorts. **CCI**

PFIZER CONFIDENTIAL

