Variable	Operational definition
	Unknown
Modified Charlson comorbidity index (CCI)	Documented histories of comorbidities using condition categories based on a modified Charlson Comorbidity Index (CCI) and captured from unstructured documents any time prior to start of IL therapy for MBC.
CCI	[REDACTED]
Longitudinal treatment patterns	From index treatment date to death or end of follow-up
Lines of therapy	Lines of therapy in the metastatic setting are assigned by Flatiron based exclusively on abstracted data to evaluate systemic treatment on or after the MBC date.
	The start of the first line of therapy is defined as the first episode of an eligible therapy that is given after or up to 14 days before index MBC diagnosis and after the patient's start of structured activity.
	The definition of a line of therapy is generally the first eligible drug episode plus other eligible drugs given within 28 days. However, a 60-day time threshold is employed before advancing the line of therapy when CDK4/6i treatment is added to treatment with Aromatase Inhibitor (AI).
	The line number is only advanced with an addition of a new drug after the 28-day line definition period.
	The end of a line of therapy is defined as the date of last patient-level structured activity, death, or the day before the start date of the next line of therapy, whichever occurred first.
Initial prescribed dose	Palbociclib: 125 mg, 100 mg, 75 mg
Dose adjustment	Dose strength other than initial/previous prescription
Type of the first dose change	Dose reduction 125 mg to 100 mg, 125 mg to 75 mg, 100 mg to 75 mg Dose increase 75 mg to 100 mg, 100 mg to 125 mg, 75 mg to 125 mg
Time to the first dose change	Days from index date to first dose change.
Number of dose adjustment	Number of dose reduction and number of dose increase over the calendar time (quarter since February 2015) and over treatment cycle since index date
Reasons for discontinuation	Disease progression, toxicity, financial, patient request, other
Duration of treatment	Days from index prescription order date to end of treatment, start of subsequent line of therapy, or death from any cause, whichever

PFIZER CONFIDENTIAL

Variable	Operational definition
Combination endocrine partner	occurred first Letrozole, Anastrozole, Exemestane

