Dose adjustment	Describe dose changes of Palbociclib from initiation to discontinuation. Sankey diagram will be used as appropriate. Factors associated with dose adjustment will be examined by univariate and multivariate analyses as appropriate. Clinical outcomes (i.e, rwPFS, OS, and tumor response) associated with dose adjustment will be explored by Kaplan-Meier Plot, Cox regression, or logistic regression as appropriate.

PFIZER CONFIDENTIAL

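### The planned OS subgroups include subsequent treatments, a factor that arises after the index date and that treatment can change, so those subgroup hazard ratios are not treatment effects (minor)

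*Protocol*

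**What the plan says.** Protocol 9.7.4.5 states that subgroup analyses will be done by age, minority status, ECOG, de novo disease, metastatic pattern and number of sites, and then "endocrine sensitivity, endocrine AI partner, comorbidities, subsequent treatments as appropriate based on availability of the data and sample sizes". SAP 4.2 repeats the list. The qualifier concerns data availability and sample size. It does not address when a factor is measured.

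The matching objective is descriptive only (Protocol 8): "To describe treatment patterns of Palbociclib, including initial dose, dose adjustment, treatment duration, subsequent treatments, and time to chemotherapy". Protocol 9.3 and SAP 5.1 record treatment patterns from the index date until death or end of follow-up.

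On dose adjustment, SAP 7.3 says: "Clinical outcomes (i.e, rwPFS, OS, and tumor response) associated with dose adjustment will be explored by Kaplan-Meier Plot, Cox regression", or logistic regression, as appropriate. No rule says from what time a patient counts as adjusted. The date needed for such a rule is already defined in SAP 5.1: "Days from index date to first dose change". The only mention of time-dependent covariates, in SAP 7.1, belongs to the check of proportional hazards.

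**The concern.** A subgroup HR estimates a treatment effect only if subgroup membership is settled before treatment can act on it. Whether, when and which later therapy a patient receives depends on how long first-line treatment held the disease and on whether the patient lived long enough to move on. If palbociclib delays second-line treatment, the patients without subsequent treatment on palbociclib differ from those on AI alone, and so do the patients with it. Weighting on baseline covariates does not repair this, because the selection happens after baseline.

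The dose-adjustment row has a related gap. A patient must stay alive and on drug to have an adjustment. If patients were classed from the index date as ever or never adjusted, the adjusted group would be credited with survival time that it had to have.

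At stake is a published subgroup or exploratory result that looks like effect modification, or like a benefit of adjustment, when neither exists.

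**Working it through.** The plan gives no figure for this point, so there is none to reproduce. The check asks how far the HRs move when nothing is going on.

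**Subsequent treatments: inputs**
- OS: exponential, median 40 months in both arms (AI-alone assumption, Protocol 9.7.2). Monthly hazard ln 2/40 = 0.0173; true HR 1.00.
- Start of second line: exponential, medians 11.9 (AI alone) and 20.0 months (palbociclib + AI). These are the earlier study's rwPFS figures in Protocol 7, "median rwPFS (20.0 vs 11.9 months; hazard ratio, 0.58", used as a proxy (assumption). Monthly hazards: ln 2/11.9 = 0.0582 and ln 2/20.0 = 0.0347.
- Follow-up: uniform from 6 to 68 months (index February 2015 to March 2020, cutoff 30 September 2020). Uniform entry is an assumption. The follow-up row in Protocol 9.1 gives 2021 as the cutoff year; 2020 is used here because the eligibility criteria use it.
- Arms 1:1. A Gaussian copula links the times to second line and to death; its correlation is assumed and varied.
- With subsequent treatment = second line starts before death and before cutoff. The split is an assumption, since the plan does not define the levels.

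**Result: Cox HR, palbociclib + AI versus AI alone, no true effect**

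| Correlation | All patients | With | Without |
|---|---|---|---|
| 0 | 1.00 | 0.90 | 0.73 |
| 0.3 | 1.00 | 0.96 | 0.77 |
| 0.6 | 1.00 | 1.02 | 0.86 |
| 0.8 | 1.00 | 1.10 | 1.08 |
| 0.9 | 1.00 | 1.15 | 1.73 |

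Repeat runs agree to about 0.01, except for the last cell (1.69 to 1.73). For correlations of 0 to 0.6, 52–53% of palbociclib patients and 67–71% of AI-alone patients fall in the level with subsequent treatment. That difference between arms is the selection. As a control, with second-line medians of 11.9 months in both arms, both subgroup HRs return to about 1.00 (0.99 to 1.01).

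With the randomised trial's medians as proxy ("With extended follow-up, the median PFS was 27.6 vs 14.5 months"), correlations of 0 to 0.6 give 0.89–1.06 with and 0.72–0.87 without.

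**Dose adjustment: illustration, if grouped ever/never from index**
- Assumed: 30–50% of patients prone to adjustment; median 3–12 months to adjustment, possible only while on drug; median time on drug 20 months; no effect of adjustment on death.
- OS median 50 months (Protocol 9.7.2).
- Ever-versus-never OS HR: about 0.67 to 0.85. With wider assumptions (30–60% prone, median 2–12 months, adjustment possible at any time): 0.51 to 0.88.
- A time-dependent covariate returns 1.00 and a 6-month landmark 0.99 to 1.01.
- Cost of that landmark: deaths by month 6 are 1 − 2^(−6/50) = 8.0% of patients. Deaths by cutoff are 1 − [50/(62 × ln 2)] × (2^(−6/50) − 2^(−68/50)) = 1 − 1.163 × (0.920 − 0.390) = 38%. So about 8.0/38 = 21% of OS events fall before the landmark.

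**The case against.** The plan never defines the levels. Subsequent treatments could mean the type of next therapy rather than with versus without, so the table shows one reading and is not the planned analysis. That stands. It does not rescue the factor, because type of next therapy is also settled after index.

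The sign of the bias depends on an unknown correlation. This stands too. A reader who looked only at correlations up to 0.6 might infer that the subgroup without subsequent treatment always flatters palbociclib. At 0.8 and 0.9 it does not.

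The abstract's shorter subgroup list, which ends "metastatic site (i.e. visceral, bone only, etc.), and endocrine sensitivity as sample sizes allow", leaves subsequent treatments out. It would be tempting to read that as a contradiction within the protocol. But the abstract also omits de novo disease, AI partner and comorbidities, so it is probably just abbreviated and carries little weight.

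SAP 3.2 says "No adjustments for multiple comparisons will be made", which may suggest subgroup tests at an unadjusted 0.05. That rule follows the two OS hypotheses in SAP 3.1, and neither document specifies a subgroup test, so no false-positive rate is claimed here.

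On dose adjustment, the SAP calls the work exploratory, Protocol 9.9 already disclaims causality, and a Cox model can take a time-dependent exposure. All true. Grouping by ever/never is not stated; it is only not excluded. What remains is a missing specification.

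**Conclusion.** The point holds as a minor one, limited to subgroup and exploratory analyses. Both documents commit to subgrouping the treatment comparison by a post-index factor that treatment can change. The resulting HRs cannot be read as treatment effects, and neither the direction nor the size of the error can be known in advance. The numbers rest on the assumed with/without split, exponential times, rwPFS as proxy for second-line start, and an assumed correlation. The conclusion that the subgroup HR is not a treatment effect does not depend on them, but the size does. The distortion disappears in the model if time to second line is the same in both arms, which the earlier results quoted in the protocol give no reason to expect.

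Two stronger readings are not supported. First, the primary weighted OS comparison does not condition on subsequent treatment or dose adjustment, so it is not affected. Second, a reader might extend the argument to the rule that lets palbociclib added within 60 days of AI start count as first-line combination. Protocol 9.1 and 9.3 together put the index at the first drug of the line. With no true effect, the OS HR moves only to 0.96–0.99 when 10–50% of palbociclib patients add it late (assumed). Analyses with another window are already planned in Protocol 9.7.4.4 and SAP 7.2. No change is asked for there.

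**What to change.** 1. Delete subsequent treatments from the subgroup lists in Protocol 9.7.4.5 and SAP 4.2, and report them descriptively by arm, as the secondary objective asks. The cost is one list item in each document; no valid treatment comparison is lost.
2. In the dose-adjustment row of SAP 7.3, state that for OS and rwPFS adjustment enters as a time-dependent covariate, using the time to first dose change already defined, or that a fixed landmark is used. This is a wording change and needs no new data. Confounding by the reason for the adjustment remains under either method. A landmark also loses early events: about 21% of OS events at 6 months under the assumptions above.

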9.8. Quality control

This is a retrospective study, therefore issues of quality control at study sites, e.g. data clarification queries, do not apply. Analyses are programmed according the specifications in the protocol's SAP and all code and other technical artifacts are documented and stored following established programming practices on Pfizer servers and in Pfizer's Global Document Management System. Quality control (QC) will follow the Flatiron's standard procedure for quality control and assurance as described in Flatiron Health Analytic Database Parent Protocol. QC for structured and unstructured data is conducted prior to delivery of each dataset. For each data model, Flatiron generates and continually maintains a set of quality standards and versioned business rules. These QC standards cover themes such as demographics, biomarkers, treatment, therapy shares, treatment length/dosage, lines of therapy, real-world recurrence, and real-world progression free survival. They have a team of

900 expert nurse and physician abstractors that co-create and version rules, and also to create QC that includes both medical considerations (e.g. what are expected based on the literature and clinical practice) and data considerations (e.g. stability from prior months). Missingness of death data is a major confounding factor for many real-world oncology analyses. For survival data, Flatiron Health utilizes 4 resources, including the National Death Index, US Social Security Death Index, obituaries, and commercial death data published from a vendor to identify when patients have died (https://onlinelibrary.wiley.com/doi/full/10.1111/1475-6773.12872). In a study of advanced non-small cell lung cancer patients, sensitivity increased from 66% from Flatiron's EHR-based registry alone to over 91% from the composite of the 4 sources.

QC will be performed for the results of the study, including reviewing and double checking for correct data, consistency, spelling, grammar, and structure. It is also reviewed to ensure that it conforms to Flatiron's data dictionary, has internal consistency (e.g. that date of diagnosis occurs after date of birth) and meets the study objectives. The final review of the findings and content will be conducted in a summary presentation.

9.9. Limitations of the research methods

Given the retrospective nature of the study, some limitations are present including those typical of a data source where the primary purpose for collection was other than research. These include potential bias in treatment selection, incomplete or missing data, limited data on comorbidities, potential for inaccurate data capture, lack of scheduled assessments and lack of standardized assessment of tumor response or progression free survival. In addition, response to treatment and disease progression were determined based on the individual treating physician's clinical assessment or interpretation of radiographic scans or pathology results rather than a standard criterion such as RECIST.

Although IPTW will be used to balance patient characteristics and sensitivity analyses (e.g., PSM) will be conducted, other variables unavailable in the database, such as disease-free interval and prior therapy in neoadjuvant setting cannot be statistically controlled. Sample size may not be large enough for some subgroup analyses. Additionally, no causality could be made from the retrospective analysis. Moreover, these findings may not be generalizable to other patient populations.

